1.2. Study Design

Overview of Study Design and Key Features	
	The participants in overseas country will receive 1 single dose of investigational RSVPreF3 OA vaccine on Visit 1 (Day 1).
Study intervention Assignment	The study will aim to enroll approximately 2600 participants, i.e., 1800 participants in China [2:1 randomization allocation between RSV OA group (China) and Placebo group (China)], 800 participants in RSV OA group (Overseas).
Day 31 (PCA) analysis	The first analysis will be performed when immunogenicity and reactogenicity data up to Visit 2 (Day 31) are available. This analysis will be considered as final for those data. Safety data up to database lock point will also be included into the analysis.
Month 6 Safety Analysis	An optional analysis may be conducted when safety data up to Month 6 are available.
End of Study Analysis	The final analysis will be performed when all data for the secondary endpoints of descriptive immunogenicity at Month 6, ARI surveillance and safety up to study conclusion are available.

2. STATISTICAL HYPOTHESES

Statistical hypotheses provided in [Table 5](#) are associated to the confirmatory co-primary NI objectives.

Table 5 Study null hypothesis

Null hypothesis	Description
H1	The GMT ratio for RSV-A neutralization titers (RSV OA group [Overseas] / RSV OA group [China]) is > 1.5 at 1 month post RSVPreF3 OA vaccine administration.
H2	The SRR difference for RSV-A neutralization titers (RSV OA group [Overseas] - RSV OA group [China]) is $> 10\%$ at 1 month post RSVPreF3 OA vaccine administration.
H3	The GMT ratio for RSV-B neutralization titers (RSV OA group [Overseas] / RSV OA group [China]) is > 1.5 at 1 month post RSVPreF3 OA vaccine administration.
H4	The SRR difference for RSV-B neutralization titers (RSV OA group [Overseas] - RSV OA group [China]) is $> 10\%$ at 1 month post RSVPreF3 OA vaccine administration.

GMT=Geometric mean titer; OA=Older adults; RSV=Respiratory syncytial virus; SRR=Seroresponse rate.

2.1. Multiplicity Adjustment

Each hypothesis will be tested at 2.5% (1-sided), no multiplicity adjustment is needed.

3. ANALYSIS SETS

Analysis set	Description
Screened Set	All participants who were screened for eligibility.
Enrolled Set	All participants who entered the study (who were randomized or received study intervention or underwent a post-screening study procedure). NOTE: screening failures (who never passed screening even if rescreened) and participants screened but never enrolled into the study (met eligibility but not needed to reach the target enrolment) are excluded from the Enrolled Set as they did not enter the study.
Exposed Set (ES)	All participants who received the study intervention. Analysis per group is based on the administered intervention.
Per-Protocol Set* (PPS)	All eligible participants who received the study intervention as per protocol, had immunogenicity results pre- and post-dose, complied with blood draw intervals, without intercurrent conditions that may interfere with immunogenicity and without prohibited concomitant medication/vaccination. Analysis per group is based on the administered intervention.

* Contribution of participants to Per-Protocol Set will be defined by timepoint.

3.1. Criteria for eliminating data from Analysis Sets

Elimination codes in [Table 6](#) will be used to identify participants to be eliminated from analysis. Details are provided below for the Enrolled Set, the Exposed Set (ES) and the Per Protocol Set (PPS).

3.1.1. Elimination from Enrolled Set

The following codes will be used for identifying participants to be eliminated from the Enrolled Set:

- Code 800 (Fraudulent data)
- Code 900 (Invalid informed consent)

3.1.2. Elimination from Exposed Set

The following codes will be used for identifying participants to be eliminated from the ES:

- Code 800 (Fraudulent data)
- Code 900 (Invalid informed consent)
- Code 1030 (Study intervention not administered at all)

3.1.3. Elimination from Per-Protocol Set

A participant will be excluded from the populations for analysis under the following conditions:

- For codes 800, 900, 1030, 1060, 1070, 1080, 1090 and 2010: participants will be eliminated for all visits.
- For codes 1040, 2040 and 2050: participants will be eliminated from a specific visit (at which the condition is met) onwards.
- For codes 2020 2090, 2100, 2120: participants will be eliminated at the specific visit at which the condition is met.

Table 6 List of elimination codes

Code	Condition under which the code is used	Visit / Contact (timepoints) where the code is checked	Visit from when it is applicable	Applicable for analysis set/endpoint
800	Fraudulent data	All	All	Enrolled Set, ES, PPS
900	Invalid informed consent	All	All	Enrolled Set, ES, PPS
1030	Study intervention not administered at all	Visit 1	All	ES, PPS
1040	Administration of concomitant vaccine(s) forbidden in the protocol (as defined in Section 5.2.2 of protocol)	All	From the specific visit the condition is met	PPS
1060	Randomization code was broken (Chinese participants only)	All	All	PPS
1070	Vaccine administration not according to protocol: 
 • Participant was vaccinated with the correct vaccine but containing a lower volume • Wrong replacement or study vaccine administered (not compatible with the vaccine regimen associated to the treatment number) • Route of the study vaccine is not intramuscular • Wrong reconstitution of administered vaccine 	Visit 1	All	PPS
1080	
 • Vaccine administration after a temperature deviation • Vaccine administered despite a Good Manufacturing Practices (GMP) no-go temperature deviation 	Visit 1	All	PPS
1090	Vaccine administration after expiration	Visit 1	All	PPS
2010	Protocol deviation linked to inclusion/exclusion criteria	All	All	PPS
2020	All Pre-dose results are missing	Visit 1	At the specific visit the condition is met	PPS

Code	Condition under which the code is used	Visit / Contact (timepoints) where the code is checked	Visit from when it is applicable	Applicable for analysis set/endpoint
2040	Administration of any medication forbidden by the protocol (as defined in Section 5.2.2 of protocol)	All	From the specific visit the condition is met.	PPS
2050	Intercurrent medical condition: Participants may be eliminated from the PPS for immunogenicity if, during the study, they incur a condition that has the capability of altering their immune response or are confirmed to have an alteration of their initial immune status.	All	From the specific visit the condition is met.	PPS
2090	Participants did not comply with blood sample schedule: 
 Number of days between vaccination (Visit 1) and blood sample (Visit 2) is outside [30-42] days. Number of days between vaccination (Visit 1) and blood sample (Visit 3) is outside [180-210] days. 	Visit 2, Visit 3	At the specific visit the condition is met	PPS
2100	Immunological results not available post-vaccination	Visit 2, Visit 3	At the specific visit the condition is met	PPS
2120	Obvious incoherence/abnormality or error in laboratory data 
 Unreliable released data as a result of confirmed sample mismatch or confirmed inappropriate sample handling at laboratory. 	All	At the specific visit the condition is met	PPS

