#### **6.4.1. Emergency unblinding**

This is a partial blind study in which the qualified personnel are blinded to study intervention for participants in China. The IVRS/IWRS will be programmed with blind-breaking instructions. In case of an emergency, the investigator has the sole responsibility for determining if unblinding of a participants' intervention assignment is warranted. Participant safety must always be the first consideration in making such a determination. If the investigator decides that unblinding is warranted, the investigator may, at the investigator's discretion, contact GSK to discuss the situation prior to unblinding a participant's intervention assignment unless this could delay emergency treatment for the participant. If a participant's intervention assignment is unblinded, GSK must be notified within 24 hours of this occurrence. The date and reason for the unblinding must be recorded.

If the investigator is unable to access IVRS/IWRS, they can contact the GSK helpdesk based on the information provided in the pharmacy manual.

A physician other than the investigator (e.g., an emergency room physician) or participant/participant's caregiver or family member may also request emergency access to the participant's study intervention information as per participant card.

A participant may continue in the study if that participant's intervention assignment is unblinded. The primary reason for discontinuation (the event or condition which led to the unblinding) will be recorded in the eCRF.

GSK's Global Safety staff may unblind the intervention assignment for any participant with an SAE. If the SAE requires that an expedited regulatory report be sent to 1 or more regulatory agencies, a copy of the report, identifying the participant's intervention assignment, may be sent to investigators in accordance with local regulations and/or GSK policy.

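### A Visit 1 titre confirmed as unreliable (code 2120) is still used as the baseline in the Day 31 and Month 6 per-protocol analyses

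*SAP*

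**What the plan says.** SAP 3.1.3 sorts the PPS elimination codes into three timings: all visits, from the visit concerned onwards, and the visit concerned only. The third group is defined by "For codes 2020 2090, 2100, 2120: participants will be eliminated at the specific visit at which the condition is met".

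- **Code 2120** is checked at all visits. Its condition is "Unreliable released data as a result of confirmed sample mismatch or confirmed inappropriate sample handling at laboratory".
- **Code 2020** is checked at Visit 1. Its condition is "All Pre-dose results are missing".
- **Code 1060**, a broken randomisation code, applies to participants in China only and eliminates for all visits, whenever the break occurs.

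SAP section 3 defines the PPS as participants who, among other things, "had immunogenicity results pre- and post-dose, complied with blood draw intervals". Its footnote adds: "Contribution of participants to Per-Protocol Set will be defined by timepoint".

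The Visit 1 titre enters both types of co-primary endpoint. It is the covariate in the ANCOVA for the GMT ratio (SAP 4.2.2) and the denominator of the fold rise of at least 4 that defines seroresponse (SAP 4.1.3). SAP 4.1.4 takes the latest non-missing pre-dose value as baseline. SAP 4.2.2 says that missing data are not imputed.

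**The concern.** An elimination limited to one visit suits a bad Visit 2 or Visit 3 sample, because that titre is used only at its own visit. A Visit 1 titre is different: it is carried into every later comparison that needs a baseline. Removing the participant at Visit 1 leaves the Day 31 record intact, so a value that the laboratory has disowned feeds the GMT ratio and the SRR on which non-inferiority is judged. It also feeds the mean geometric increase (MGI) and the Month 6 comparisons.

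The direction depends on where the errors fall. A wrong baseline adds noise to the fold rise. With SRRs above 50%, that noise pulls the apparent rate down. In the China group this makes non-inferiority harder to show. In the overseas group it shrinks the overseas-minus-China difference and makes non-inferiority easier to show. Errors need not balance: Protocol 10.5.4 says that overseas serum must be transferred to the laboratory in China, at a delay of about a year.

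Code 1060 raises a separate timing question, because it can remove a Day 31 titre that was valid when it was drawn.

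**Working it through.** **1. Which rule removes a bad Visit 1 titre at Day 31?**

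- SAP 3.1.3 and Table 6: 2120 at Visit 1 eliminates at Visit 1 only. Membership is set by timepoint, so Visit 2 is judged separately.
- PPS definition: asks that pre-dose results exist, not that they are valid. A released titre exists.
- SAP 4.1.4: asks only for a non-missing value.
- SAP 4.1.3: says that missing or non-evaluable measurements are not replaced, but its explicit exclusion of them is written for the descriptive analysis at each timepoint. It does not clearly reach a released titre flagged later.
- Exposed Set analysis (SAP 4.2.3): runs only if more than 5% in a group are excluded, and 2120 does not apply to that set, so the bad value would be there too.

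No rule removes it.

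**2. The plan's power, reproduced.** Inputs from SAP section 5: 800 overseas and 1800 × 2/3 = 1200 China vaccinees; 10% attrition leaves 720 and 1080. H4 (RSV-B SRR), scenario 1, assumes 76.7% overseas and 73.4% China; margin 10 points; one-sided 2.5%.

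Power = Φ[(d − 1.960 × SE0) / SE1], where SE0 is restricted to the margin.

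- d = 0.100 − (0.767 − 0.734) = 0.067
- SE1 = √(0.767 × 0.233/720 + 0.734 × 0.266/1080) = 0.0207
- SE0 = 0.0203
- Power = Φ[(0.067 − 0.0399)/0.0207] = 90.5%, as in SAP Table 7.

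Overall power for scenarios 1 to 4 comes to 90.5%, 98.3%, 99.6% and 96.0%, against the stated 90.5%, 98.2%, 99.6% and 96.0%.

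**3. Size of the 2120 effect on SRR.** Assumptions: log10 titres have SD 0.45 before and after vaccination (the SAP gives 0.45 for log10 titres); pre/post correlation ρ is 0.3 to 0.8 (not in the documents); the mislinked baseline is another pre-dose-type titre, independent of the participant's post-dose titre. The SD of the log fold rise then goes from 0.45√(2(1−ρ)) to 0.45√2, so

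apparent SRR = Φ[Φ⁻¹(p) × √(1−ρ)].

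| True SRR | ρ = 0.3 | ρ = 0.5 | ρ = 0.8 |
|---|---|---|---|
| 73.4% | 69.9% | 67.1% | 61.0% |
| 76.7% | 72.9% | 69.7% | 62.8% |

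Shift in group SRR per 1% affected: from 0.01 × (73.4 − 69.9) = 0.03 points to 0.01 × (76.7 − 62.8) = 0.14 points. Whatever the model, 1% affected cannot move the group rate by more than 1 point.

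H4 scenario 1 power at ρ = 0.8:

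- Both groups affected equally, 1% to 5%: 90.5% to 90.6%.
- China only: 89.4% (1%), 88.2% (2%), 84.1% (5%).

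In the other direction, put China exactly at the margin (66.7% against 76.7%) and let 1% of the overseas group be affected at ρ = 0.8. The overseas SRR becomes 0.99 × 76.7 + 0.01 × 62.8 = 76.6%, and the same formula gives a false-positive rate for H4 of about 2.9% instead of 2.5%.

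**4. Cost of dropping the bad baselines.** With 0.5%, 1%, 2% and 5% of both groups removed, H4 scenario 1 power is 90.4%, 90.2%, 89.9% and 89.0%. For 1%: n = 713 and 1069, Φ[(0.067 − 1.960 × 0.0204)/0.0208] = 90.2%.

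**5. Code 2020.** With no baseline, nothing is derived (SAP 4.1.4) and nothing is imputed (SAP 4.2.2), so the participant drops out of both co-primary analyses. What remains is a mismatch: Table 6 would admit these participants to the unadjusted Day 31 and Month 6 GMTs in the PPS, while the definition ("had immunogenicity results pre- and post-dose") would not.

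**6. Code 1060.** Forbidden vaccines, forbidden medication and intercurrent conditions (codes 1040, 2040, 2050), which can change immunity, eliminate only from the visit concerned onwards. A code break, which cannot change a titre already drawn, eliminates for all visits. It is not in the PPS definition, Protocol 9.2.1 or the primary estimand's intercurrent events (SAP Table 1), and Protocol 6.4.1 lets unblinded participants continue. A break after a participant's own Day 31 visit but before the Day 31 lock therefore removes a valid titre. If 1% of China vaccinees (about 11 of 1080) were removed and their SRR were 10 to 40 points lower (assumed), the China SRR would rise by 0.1 to 0.4 points.

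**The case against.** The best defence on 2120 is that the SAP is merely silent. Membership goes by timepoint, so flagging Visit 1 arguably removes that titre, and a mismatched sample could be called non-evaluable. No sentence says that such values will be used. A sensible programmer might well treat the titre as missing. But the SAP does not say so, and the literal rule gives the opposite result. A one-line clarification is therefore fair.

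Three stronger readings are tempting, and the documents do not support them.

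- *Code 2020 also puts bad baselines into the co-primaries.* It does not. A missing baseline drops out of both analyses.
- *Code 1060 is biased because it applies to China only.* The overseas arm is open label and has no code to break, so the one-sidedness follows from the design.
- *Code 1060 selectively drops Chinese vaccinees with SAEs.* Protocol 6.4.1 says "GSK's Global Safety staff may unblind the intervention assignment for any participant with an SAE", which is permission. Nothing says that every SAE is unblinded, or that unblinding by sponsor safety staff sets code 1060.

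Excluding code-broken participants from a per-protocol set is also a pre-specified choice that can be defended. The Day 31 analysis is final for its data, so only breaks known before that lock matter. If exclusions exceed 5% in a group, the Exposed Set analysis brings these participants back. All of this stands. What survives is the timing: the code reaches back over a titre drawn before the break.

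**Conclusion.** The code 2120 point holds as the text is written. A Visit 1 titre confirmed as unreliable still serves as covariate and denominator at Day 31 and Month 6. It is worth correcting because the stated rule gives a wrong result, not because it is likely to reverse the conclusion. The modelled effect is 0.03 to 0.14 SRR points per 1% affected. It nearly cancels if both groups are affected equally, and becomes noticeable only if errors are frequent and concentrated in one group. The rates, the correlation and the independence of the mislinked baseline are assumptions. A baseline swapped with a post-dose sample would do more harm per case, within the limit of 1 point per 1%. The effect on the ANCOVA GMT ratio was not quantified.

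Code 2020 is an inconsistency with no effect on the co-primaries. Code 1060 is a minor timing fault. The documents do not establish that it biases the comparison.

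**What to change.** 1. **Code 2120.** In SAP 3.1.3, Table 6 and 4.1.4, state that a Visit 1 titre flagged 2120 is set to missing for that assay. The participant then leaves every baseline-dependent analysis of that assay (ANCOVA GMT ratio, SRR, MGI) at Visits 2 and 3. Valid post-dose titres may stay in unadjusted summaries. This is narrower than eliminating the participant from all visits, which would discard good post-dose data. A 2120 finding at Visit 2 or 3 stays specific to that visit.
2. **Code 2020.** Align its timing with the PPS definition, so that Table 6 and section 3 yield the same set for the unadjusted GMTs. The wording should also say how the definition's pre-dose requirement applies to participants under item 1.
3. **Code 1060.** Apply it only from the visit at which the code is broken onwards, or keep it and add a sensitivity analysis of the co-primaries that retains code-broken participants.

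The cost is a few lines in the elimination rules, settled before the database freeze, and a negligible loss of sample. Item 3 changes a pre-specified set. If that is unwelcome at this stage, the sensitivity analysis is the lighter option.

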4. STATISTICAL ANALYSES

4.1. General Considerations

4.1.1. Treatment group names

For simplification the treatment group names RSV OA Overseas, RSV OA China, Placebo China will be used in the subsequent SAP sections and data displays:

Treatment group names in the protocol	Treatment group names in SAP & data displays
RSV OA group (Overseas)	RSV OA (Overseas)
RSV OA group (China)	RSV OA (China)
Placebo group (China)	Placebo (China)
The immunogenicity subset of the global efficacy study RSV OA=ADJ-006	RSV OA Overseas (006 study)

4.1.2. General Methodology

- Unless otherwise specified, data summaries will be presented by treatment groups when applicable, in the order of RSV OA Overseas, RSV OA China, Placebo China.
- Data summaries with both RSV OA Overseas (006 study) and RSV OA China groups will be presented in the order of RSV OA Overseas (006 study) and RSV OA China.
- Unless otherwise specified, continuous data will be summarized using descriptive statistics: n, mean, standard deviation, median, minimum, and maximum. Categorical data will be summarized as the number and percentage of participants in each category.
- Confidence intervals (CIs) will use 95% confidence level. Exact 95% CIs around proportions are derived using the method of Clopper and Pearson [[Clopper](#), 1934].

4.1.3. General Methodology for Immunogenicity

- For the purpose of immunogenicity analyses, any missing or non-evaluable immunogenicity measurement will not be replaced. The descriptive analysis performed for each assay at each time point will exclude participants with a missing or non-evaluable measurement.
- Titers below the assay cut-off (LLOQ) will be replaced by half the assay cut-off (LLOQ/2) and titers above the upper limit of quantification (ULOQ) will be replaced by the ULOQ to compute GMTs, SRRs and MGIs and treatment differences. For the display of reverse cumulative curve, titers below LLOQ and above ULOQ won't be replaced. 95% CIs for GMT and MGI will be based on a back transformation of CI for the mean of log₁₀-transformed values. 95% CI for group difference in proportion will be based on Miettinen and Nurminen confidence interval [[Miettinen](#), 1985].
- Seroresponse rate (SRR) is defined as the proportion of participants having a fold increase in neutralizing titers ≥ 4 (post-study intervention administration over pre-study intervention administration).
- The mean geometric increase (MGI) is defined as the geometric mean of the within-participant ratios of the post-vaccination titer over pre-vaccination (Visit 1, Day 1).

4.1.4. Baseline Definition

For all endpoints the baseline value will be the latest pre-dose assessment with a non-missing value, i.e., the assessment at Visit 1 (Day 1).

Unless otherwise stated, if baseline data is missing no derivation will be performed and baseline will be set to missing.

4.2. Primary Endpoints Analyses

4.2.1. Definition of endpoint/estimands

Refer to Section 1.1 for the definition of primary estimand for immunogenicity (humoral response).

4.2.2. Main analytical approach

Primary estimand analysis will be performed on the Per-Protocol Set (PPS).

RSV-A and RSV-B neutralizing group GMT ratio at 1 month after the RSVPreF3 OA vaccine administration will be computed for RSV OA Overseas group over RSV OA China group with 95% CI, using an ANCOVA model on \log_{10} -transformed titers for each neutralization assay. The model will include the treatment group (RSV OA Overseas and RSV OA China) and the baseline \log_{10} -transformed titer as covariate.

RSV-A and RSV-B neutralizing group SRR differences at 1 month after the RSVPreF3 OA vaccine administration will be computed for RSV OA Overseas group minus RSV OA China group, with 95% CI. The 95% CI will be derived using the method of Miettinen and Nurminen.

The primary analysis result will be reported using the ED60 (Estimated Dilution 60) unit.

Missing data will not be imputed.

NI for co-primary objectives will be claimed to be successful if the upper limit of the 2-sided 95% CI for the GMT ratio will be ≤ 1.5 and the upper limit of the 2-sided 95% CI for the SRR difference will be $\leq 10\%$ for both RSV-A and B.

4.2.3. Additional estimand/analysis

An additional analysis will be conducted analogously using the IU/ml unit.

If, in any group, the percentage of vaccinated participants with serological results excluded from the PPS is more than 5%, a second analysis based on the ES will be performed to complement the PPS analysis.

4.3. Secondary Endpoints Analyses

Refer to Section 1.1 for the definition of the estimands for secondary endpoints.

4.3.1. Secondary Immunogenicity

All between groups analyses of secondary endpoints presented in this section will be descriptive with the aim to characterize the difference in immunogenicity between groups. These descriptive analyses should be interpreted with caution considering that there is no adjustment for multiplicity for these comparisons.

4.3.1.1. Humoral immune response in RSV OA (Overseas) group and RSV OA (China) group

The analysis will be performed on the Per-Protocol Set. If, in any group, the percentage of vaccinated participants with serological results excluded from the PPS is more than 5%, a second analysis based on the ES will be performed to complement the PPS analysis.

